4.1 Type/Design of Trial

This is a 12-week, multicenter, open-label trial designed to evaluate the safety and tolerability of brexpiprazole treatment in adult subjects diagnosed with BPD. Subjects will receive 2 to 3 mg/day brexpiprazole.

Enrollment into the trial will be drawn from eligible subjects who completed the last treatment visit of the previous double-blind brexpiprazole BPD trials (and took the investigational medicinal product [IMP] through the last scheduled treatment visit) and, in the investigator's judgment, could potentially benefit from treatment with brexpiprazole for BPD.

The trial will be organized as follows:

Screening/Baseline: Subjects will be screened for eligibility at the last scheduled treatment visit of the previous double-blind trial. Subjects will sign a separate informed consent form (ICF) at the last scheduled treatment visit of the previous double-blind trial for participation in this trial before any procedures specific to the open-label trial are performed. The assessments from the last scheduled treatment visit of the previous double-blind trial will serve as the baseline measures for this trial for any assessment that is not new (unique) to the open-label trial. Medical history will be updated, if necessary. Informed consent cannot be obtained after the last scheduled treatment visit of the previous double-blind trial without all screening/baseline assessments being repeated. If a subject is unable to rollover immediately, up to 3 days may be permitted between the end of the double-blind trial and the start of IMP in the open-label extension trial; however, this must be discussed with the medical monitor (Note: assessments from the last scheduled treatment visit in the previous double-blind trial that are going to be used as the baseline measures for Trial 331-201-00195 will not need to be repeated if the subject enters Trial 331-201-00195 within 3 days).

Treatment Phase: Eligible subjects will receive daily treatment with open-label brexpiprazole beginning at the screening/baseline visit, as described in [Section 6.1](#). Visits will occur at the end of Weeks 2, 4, 8, and 12. Telephone contact will be made at Weeks 1, 6, and 10 to assess adverse events (AEs) and concomitant therapy. In addition, an optional telephone call or other form of communication will be made with the subject approximately 1 week (\pm 2 days) after the visit (eg, at Weeks 3, 5, 7, 9, and 11) to check on status. All subjects will receive up to 12 weeks of open-label treatment in this trial.

Follow-up: Subjects will be followed for safety via telephone contact or clinic visit 21 (\pm 3) days after the last dose of open-label brexpiprazole.

See Figure 1.2-1 for a schematic of the trial design.

4.2 Scientific Rationale for Trial Design

Given its clinical efficacy in treating both schizophrenia and MDD as well as its multimodal mechanism of action, brexpiprazole may offer added benefit to patients suffering from BPD. Like other psychological disorders, BPD has been linked to aberrations in monoaminergic neurotransmission. While dysfunctions related to dopamine and serotonin have been historically cited, recent evidence has also implicated noradrenergic dysfunction in BPD as well.^{19,20,21,22}

While the precise mechanism of action of brexpiprazole in treating psychiatric conditions is unknown, the pharmacology of brexpiprazole is believed to be mediated by a combination of high-binding affinity and functional activities at multiple monoaminergic receptors, as noted in [Section 2](#). Together, the broad pharmacological profile of brexpiprazole may provide for a unique treatment strategy for BPD. More specifically, the serotonergic and dopaminergic stabilization and modulation provided by brexpiprazole may directly address some of the key features and symptoms noted in the disease including impulsivity, aggression, affective instability, and suicidality. It is anticipated that the brexpiprazole safety profile for BPD will be comparable to the safety profiles of the currently approved indications.

Trial 331-201-00195 is being conducted to evaluate the safety and tolerability of brexpiprazole in subjects diagnosed with BPD who have completed a double-blind BPD trial.

4.3 Dosing Rationale

The dosing paradigm of brexpiprazole to be used in Trial 331-201-00195 has been determined based on the dosing ranges investigated in other related psychiatric indications (bipolar I disorder, MDD, PTSD, and schizophrenia) and the dosing ranges used in the previous double-blind trials for the open-label extension.¹⁰

In other psychiatric indications, brexpiprazole has been shown to be safe and well tolerated within the proposed dose range to be investigated in this trial (ie, 2 to 3 mg/day). In addition, the effective dose range for approved indications (MDD and schizophrenia) is 2 to 4 mg/day; the 1 mg/day dose has not been shown to be effective.

4.4 End of Trial Definition

The end of trial date is defined as the last date of contact or the date of final contact attempt from the post-treatment follow-up page in eSource for the last subject completing or withdrawing from the trial.

4.5 Definition of Completed Subjects

The treatment period is defined as the time period during which subjects are evaluated for primary and/or secondary objectives of the trial irrespective of whether or not the subject actually consumed all doses of the IMP. Subjects who are evaluated at the last scheduled visit during the treatment period will be defined as trial completers. For purposes of this trial, subjects who complete Week 12 visit will be defined as trial completers.

5 Trial Population

The trial population will consist of eligible male and female subjects diagnosed with BPD and who, in the investigator's judgment, could potentially benefit from treatment with brexpiprazole for BPD according to the following criteria:

- Subjects who participated in a double-blind brexpiprazole BPD trial will be eligible for Trial 331-201-00195 if they have completed the last scheduled treatment visit of the previous double-blind trial and did not terminate early.
- Subjects must qualify for Trial 331-201-00195 at the last scheduled treatment visit of the previous double-blind trial and must be able to continue treatment without interruption between the double-blind and open-label trials (if a subject is unable to rollover immediately, up to 3 days may be permitted between the end of the double-blind trial and the start of IMP in the open-label extension trial; however, this must be discussed with the medical monitor).

Decisions regarding inclusion of subjects at the time of enrollment and assessment of subject safety throughout the trial primarily remain at the discretion of the investigator; however, the medical monitor may recommend exclusion or discontinuation of a subject based on individual subject data.

5.1 Subject Selection and Numbering

All subjects will retain a unique subject identifier (ID; site number [3 digits] + subject number ['S' + 5 digits] that was given upon providing consent [or assent if applicable]) for the previous double-blind trial.

5.2 Eligibility Criteria

Exceptions for eligibility criteria will not be permitted during the trial, neither by the investigator nor by the medical monitor.

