4) Subjects with abnormal laboratory tests results, vital signs results, or electrocardiogram (ECG) findings, unless, based on the investigator’s judgment, the findings are not medically significant and would not impact the safety of the subject or the interpretation of the trial results. The medical monitor should be contacted to discuss individual cases, as needed.

In addition, subjects with the following laboratory test and ECG results at screening must be excluded from the trial:

- Platelets $\leq 75000/\text{mm}^3$
- Hemoglobin $\leq 9 \text{ g/dL}$
- Neutrophils, absolute $\leq 1000/\text{mm}^3$
- Aspartate aminotransferase (AST) $> 2 \times$ the upper limit of normal (ULN)
- Alanine aminotransferase (ALT) $> 2 \times$ ULN
- Creatine phosphokinase (CPK) $> 3 \times$ ULN, unless discussed with and approved by the medical monitor
- Creatinine $\geq 2 \text{ mg/dL}$
- QT interval corrected for heart rate using Fridericia’s formula (QTcF) $\geq 450 \text{ msec}$ in men and $\geq 470 \text{ msec}$ in women, unless due to ventricular pacing.

Tests with exclusionary results should be repeated to ensure reproducibility of the abnormality before excluding a subject based on the criteria noted above. For ECGs, perform 3 consecutive recordings. If 2 of the 3 remain exclusionary then the subject must be excluded.

- 5) Subjects with a positive drug screen for cocaine or other illicit drugs are excluded and may not be retested or rescreened. Subjects with a positive urine drug screen resulting from use of cannabis, or prescription or over-the counter medications, or products that, in the investigator's documented opinion, do not signal a clinical condition that would impact the safety of the subject or interpretation of the trial results may continue evaluation for the trial following consultation and approval by the medical monitor. Subjects with positive results for alcohol use will require consultation and approval by the medical monitor in order to verify use does not indicate a substance-use disorder.

Other

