8.7.1 Clinical Laboratory Assessments

Clinical laboratory samples will be collected at the time points described in the schedule of assessments (Table 1.3-1) to perform the clinical laboratory assessments described in [Section 10.2](#). Refer to [Section 10.5](#) for criteria for identifying laboratory values of potential clinical relevance.

A central laboratory designated by the sponsor will be used for all laboratory testing (hematology [including HbA1c], serum chemistry [including prolactin], and urinalysis) required during the trial. The central laboratory should be used for all laboratory testing whenever possible (including unscheduled and follow-up, if needed). In cases where an immediate result is required for a particular laboratory test, the sample should be divided and sent to both a local laboratory and the designated central laboratory. Subjects should be fasting for a minimum of 8 hours prior to the blood draws, if possible. If fasting blood samples are not feasible at screening/baseline, nonfasting blood samples may be obtained initially for determining eligibility for the trial and need to be repeated at the next visit at the discretion of the investigator. Additional urine and blood samples may be collected for further evaluation of safety as warranted by the investigator's judgment. Reports from the central laboratory should be filed with the source documents for each subject. The central laboratory will provide laboratory results to the sponsor electronically.

Any value outside the normal range will be flagged for the attention of the investigator who must indicate whether or not a flagged value is of clinical significance. If one or more values are questionable, the test(s) may be repeated. If the result of any test (or repeat test, if done) is indicated as clinically significant in the samples taken at screening/baseline, the subject will NOT be enrolled into the trial without the permission of the medical monitor. In addition, unscheduled laboratory tests should be performed if clinically significant abnormalities are observed. Unscheduled laboratory tests may be repeated at any time at the discretion of the investigator for appropriate medical care.

Refer to Appendix 5 ([Section 10.5](#)) for criteria for identifying values of potential clinical relevance.

The total volume of blood to be collected during the trial will be documented in the ICF.

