8.7.4 Electrocardiogram

Electrocardiograms will be performed at the time points described in the schedule of assessments (Table 1.3-1). Subjects should be monitored for potentially clinically significant ECG results ([Section 10.7](#)).

Electrocardiogram recordings will be obtained after the subject has been supine and at rest for at least 5 minutes. Additional ECGs may be obtained at the investigator's discretion and should always be obtained in the event of an ET. The principal investigator

(or qualified designee) will review, sign, and date each ECG reading, noting whether or not any abnormal results are of clinical significance. The ECG will be repeated if any results are considered to be clinically significant. A central ECG service will be used for reading all ECGs in order to standardize interpretations for the safety analysis.

Rollover subjects will be enrolled in trial based on the screening/baseline ECG results from the trial site. If at screening/baseline, according to the investigator's judgment, any abnormal ECG finding is deemed medically significant (impacting the safety of the subject or the interpretation of the trial results), the subject should be excluded from the trial. Abnormal results for ECGs should be repeated once at screening/baseline with 3 consecutive ECG recordings to ensure reproducibility of the abnormality before excluding a subject based on the criteria noted above. Each ECG recording should be taken approximately 5 minutes apart (the ECG result reported will be evaluated at each time point). The central ECG service will provide the corrections for the 3 ECGs performed. If the screening/baseline ECG results from the central reader, when available, indicate a QTcF \geq 450 msec in men and \geq 470 msec in women (unless due to ventricular pacing at screening/baseline), the investigator must contact the medical monitor to discuss the subject's continued participation in the trial.

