Appendix 3**Criteria for Identifying ECG Measurements of Potential Clinical****Relevance**

Variable	Criterion Value ^a	Change Relative to Baseline ^a
Rate		
Tachycardia	≥ 120 bpm	increase of ≥ 15 bpm
Bradycardia	≤ 50 bpm	decrease of ≥ 15 bpm
Rhythm		
Sinus tachycardia ^b	≥ 120 bpm	increase of ≥ 15 bpm
Sinus bradycardia ^c	≤ 50 bpm	decrease of ≥ 15 bpm
Supraventricular premature beat	all	not present → present
Ventricular premature beat	all	not present → present
Supraventricular tachycardia	all	not present → present
Ventricular tachycardia	all	not present → present
Atrial fibrillation	all	not present → present
Atrial flutter	all	not present → present
Conduction		
1° atrioventricular block	PR ≥ 200 msec	increase of ≥ 50 msec
2° atrioventricular block	all	not present → present
3° atrioventricular block	all	not present → present
Left bundle-branch block	all	not present → present
Right bundle-branch block	all	not present → present
Pre-excitation syndrome	all	not present → present
Other intraventricular conduction block ^d	QRS ≥ 120 msec	increase of ≥ 20 msec
Infarction		
Acute or subacute	all	not present → present
Old	all	not present → present
		≥ 12 weeks post study entry
ST/T Morphological		
Myocardial Ischemia	all	not present → present
Symmetrical T-wave inversion	all	not present → present
Increase in QTc	QTcF ≥ 450 msec (men) QTcF ≥ 470 msec (women)	

^a In order to be identified as potentially clinically relevant, an on-treatment value must meet the “Criterion Value” and also represent a change from the subject’s baseline value of at least the magnitude shown in the “Change Relative to Baseline” column.

^b No current diagnosis of supraventricular tachycardia, ventricular tachycardia, atrial fibrillation, atrial flutter, or other rhythm abnormality.

^c No current diagnosis of atrial fibrillation, atrial flutter, or other rhythm abnormality.

^d No current diagnosis of left bundle branch block or right bundle branch block.

12 Proposed List of Summary Tables

- CT-1.1 Subject Disposition (Enrolled Sample)
- CT-1.2 Subject Disposition by Center (Enrolled Sample)
- CT-1.3 Subject Completion Rates by Week (Enrolled Sample)
- CT-1.4 Enrollment by Country (Enrolled Sample)
- CT-1.5 Enrollment by Country by Age Group (Enrolled Sample)
- CT-1.6 Summary of Proportion of the Face-to-Face and Virtual Visits by Study Week (Enrolled Sample)
- CT-2 Reasons for Discontinuation (Enrolled Sample)
- CT-3.1 Demographic Characteristics (Enrolled Sample)

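### Section 5.2 and criterion 4 allow no medical-monitor exception for a clinically significant entry laboratory result (CPK aside), but section 8.7.1 implies one; the deciding QTcF reading and the SAP's QTc-increase row also need to be settled

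*Protocol*

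**What the plan says.** **Laboratory results at entry**

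- Protocol 5.2: "Exceptions for eligibility criteria will not be permitted during the trial, neither by the investigator nor by the medical monitor".
- Protocol 5.2.2, criterion 4, general clause: an abnormal laboratory, vital sign or ECG result excludes the subject unless, in the investigator's judgment, "the findings are not medically significant and would not impact the safety of the subject or the interpretation of the trial results".
- Criterion 4, listed limits: "In addition, subjects with the following laboratory test and ECG results at screening must be excluded from the trial". Eight limits follow, seven laboratory and one ECG. CPK alone carries the words "unless discussed with and approved by the medical monitor".
- Protocol 8.7.1: where any screening/baseline test, or its repeat, is marked clinically significant, "the subject will NOT be enrolled into the trial without the permission of the medical monitor".

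**ECG at entry**

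- Criterion 4 sets QTcF limits of 450 msec or more in men and 470 msec or more in women, excused only by ventricular pacing. Exclusion is required if two of three repeat recordings remain over the limit.
- Footnote m of Table 1.3-1 and section 8.7.4 make the site's screening/baseline ECG the basis for enrolment.
- Section 8.7.4 also has the central service supply the corrections for the three repeat recordings. If the central reading, once available, meets the same QTcF limits ("unless due to ventricular pacing at screening/baseline), the investigator must contact the medical monitor to discuss"), the subject's continued participation is discussed.

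**QTc row in the safety tables**

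- SAP Appendix 3 gives the row for an increase in QTc the criterion "QTcF ≥ 450 msec (men) QTcF ≥ 470 msec (women") and leaves its change-from-baseline cell blank. Footnote a of the same table requires both a criterion value and a change. Protocol Appendix 7 has the same blank cell, with its limits written as strictly above 450 and 470 msec.

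**The concern.** Entry limits in a safety trial should have one meaning. If one section forbids exceptions and another makes entry depend on the medical monitor's permission, two sites can both follow the protocol and decide the same case differently. The ECG text raises a related question, because the QTcF limits in criterion 4 and in 8.7.4 are the same but the consequences differ.

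The QTc row is a separate matter of reporting. A row that is named for an increase but has no change condition can count a subject whose QTcF has not moved.

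**Working it through.** No figure in the plan can be reproduced here, since the sample size is not power-based and the point concerns wording. The check sets the passages side by side and runs test cases through them.

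**1. Which medical-monitor routes stand inside the criteria.** Of the seven laboratory limits (platelets, hemoglobin, neutrophils, AST, ALT, CPK, creatinine), one has such a route: CPK. That leaves 7 − 1 = 6 without one. The QTcF limit has a pacing exception but no medical-monitor route. Criteria 3, 5 and 6 write the medical monitor's role into the criterion itself (suicidal ideation item 4, some positive drug screens, COVID-19 deviations). So the protocol's usual practice is to put such a route inside the numbered criterion. The 8.7.1 route is outside, and criterion 4 does not refer to it.

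**2. Laboratory test cases.** I take clinically significant (8.7.1) and medically significant (criterion 4) to mean the same.

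| Case | 5.2 and criterion 4 | 8.7.1 |
|---|---|---|
| Result not on the list, confirmed and judged clinically significant | Excluded, because the general clause excuses only findings that are not medically significant | Not enrolled unless the medical monitor permits |
| ALT 2.5 × ULN, confirmed and clinically significant (limit: above 2 × ULN) | Must be excluded | Not enrolled unless the medical monitor permits, if 8.7.1 is read to cover listed limits |

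The first case conflicts whatever is decided about the list. The second conflicts only if permission under 8.7.1 is taken to be enough against a listed limit. The clause covers any test and does not set the list aside.

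**3. ECG test case.** A man has a site QTcF of 445 msec and a central QTcF of 455 msec on the same screening ECG.

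- On the site reading, 445 < 450, so he meets criterion 4 and may be enrolled.
- On the central reading, 455 ≥ 450, so 8.7.4 sends his continued participation to discussion.
- Section 6.1 expects the first open-label dose one day after the last double-blind dose, so the central reading may come after dosing.

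No limit has been overridden at enrolment. What the text leaves open is which reading criterion 4 itself means. For the repeat rule, 8.7.4 points to central corrections although enrolment rests on the site.

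**4. The QTc row.** I take the blank cell to mean that no change is required. Section 8.7.4 has the central service read all ECGs for the safety analysis, so this man's analysis baseline is 455 msec. Suppose Week 12 is also 455 msec.

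- Change: 455 − 455 = 0 msec.
- SAP Appendix 3: 455 ≥ 450, so he is counted in CT-12.2.2.
- SAP 9.4 new-onset category: he was already at or above 450 at baseline, so he is not counted in CT-12.3.2.

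A man admitted under the pacing exception with the same values gives the same result. If the blank cell instead means that some change is required, the amount is undefined and the row cannot be programmed.

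**The case against.** The strongest case is that the protocol already works if read as a whole.

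- **8.7.1 restricts rather than permits.** It makes the medical monitor's permission necessary; it does not say that permission is sufficient against a listed limit. The more specific list could be taken to prevail, and criterion 4 already has the medical monitor consulted on individual cases. This stands as far as it goes, so a reader should not infer that the mandatory limits are not mandatory. It does not remove the conflict with the general clause, which has no route for a finding judged medically significant.
- **8.7.4 is not an entry exception.** A reader might infer that it lets subjects over the QTcF limit into the trial. The documents do not support this: they name the site ECG as the basis for enrolment, and 8.7.4 then governs continuation. Only the missing cross-reference and the source of the repeat corrections remain.
- **10.1.5 does not make compliant sites deviate.** A reader might infer that a site using 8.7.1 or 8.7.4 commits a significant deviation. Section 10.1.5 concerns deviations arising from emergency, accident or mistake. A site that follows the text as written is not clearly in that class.
- **The QTc row is not a result of the eligibility conflict.** This is correct. Criterion 4 itself admits paced subjects over the limit, so the row would count unchanged values even with perfect enforcement. The SAP's new-onset and increase categories also let a reader separate persistent from new prolongation. The row in CT-12.2.2 is still misleading under its own name.

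**Conclusion.** The laboratory conflict holds. Section 5.2 and criterion 4 allow no medical-monitor route for a clinically significant result other than the one written for CPK, and 8.7.1 implies one for any test. It rests on treating clinically and medically significant as equivalent and, for listed limits only, on reading permission as sufficient.

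The ECG part is a clarification: enrolment has a named reading, but criterion 4 does not say whether its limit and its repeat rule use it.

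The QTc row is a separate, real defect in a descriptive safety table.

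The size is limited to those cases: opposite entry decisions for the same subject, and a row counted with 0 msec change. The documents give no frequency for either, and I assume none.

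**What to change.** 1. **Laboratory rule.** Reconcile 5.2, criterion 4 and 8.7.1 into one rule. Any medical-monitor route should stand inside the numbered criterion, as the CPK route does. Which rule prevails is for the sponsor to decide.
2. **ECG rule.** State in criterion 4 which reading, site or central, applies to the QTcF limit and to the two-of-three repeat rule, and align it with 8.7.4. That choice is also the sponsor's.
3. **QTc row.** In SAP Appendix 3, count the row only in subjects below the limit at baseline, as the SAP 9.4 new-onset categories do. Carry the condition into Protocol Appendix 7 and use the same inequality in both.

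The cost is an amendment to protocol wording in a few sections, one SAP table cell or footnote, and one programming condition. No new data are needed. A few subjects may be handled differently at entry, depending on the rule the sponsor adopts. The SAP change can be made on its own.
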